- Evaluate safety at the dose(s) used to assess imaging feasibility and select the dose(s) and imaging schedule(s) postdose that are safe and provide optimal imaging of solid tumors and metastatic lymph nodes; the dose and time postdose chosen for the detection of primary tumors and metastatic lymph nodes may be the same or different

Part 2 Primary Objective:

Verify the safety and diagnostic performance of ONM-100 compared to standard pathology at the dose(s) and imaging schedule(s) postdose selected from Part 1 for the detection of the primary tumors and the metastatic lymph nodes in a variety of solid cancers (which may include

Part 1 and Part 2 Secondary Objective

Evaluate the PK profile of ONM-100 at the dose(s) and imaging schedule(s) postdose used to assess
optimal imaging in Part 1 and Part 2

Part 3 Objective:

 To assess the safety and efficacy (sensitivity and positive predictive value [PPV]) of ONM-100 at a dose of 1 mg/kg for intraoperative imaging during head and neck squamous cell carcinoma (HNSCC) surgery, administered at 24 ±8 hours prior to surgery.

Part 3 Primary Endpoints:

- Sensitivity: True Positive Biopsies / (True Positive + False Negative Biopsies)
- PPV: True Positive Biopsies / Tumor Positive Biopsies + False Positive Biopsies

Part 3 Secondary Endpoints:

- Proportion of patients with at least one clinically significant event identified during surgery (occult disease detected, positive margin)
- Number of margins identified by ONM-100 and NIR imaging that could not be observed with white light and palpation alone
- Detection rate of HNSCC between ONM-100 fluorescence at time of surgery versus frozen sections determined by final pathology report
- Detection of positive margins at time of surgery that triggers subsequent biopsy
- Re-resection rate

Part 3 Exploratory Endpoints:

Study Design:

This is a non-randomized, open-label, multi-center, safety, PK, and imaging feasibility study of ONM-100, an intraoperative fluorescence imaging agent. The study consists of 3 parts (Parts 1, 2 and 3).

Part 1 will be performed in a dose-escalation design (maximum of 5 cohorts of 3 patients each) to
determine the dose(s) at which ONM-100 fluorescence can be used to image metastatic lymph nodes
and primary tumors in patients with HNSCC and breast cancer undergoing routine surgery at 3 ±2
hours, and if needed at an alternate imaging schedule postdose.

- Part 2 will be a verification of the dose(s) and imaging schedule(s) from Part 1. Approximately 10 to 20 patients will be enrolled in Part 2. Eligible patients will have a confirmed diagnosis (or high clinical suspicion in the opinion of the Investigator) from among the following list of solid tumor types
 Initial enrollment will begin with prostate and ovarian cancer patients only. Eligible tumor types will be opened and/or closed to enrollment based on continuous review of imaging results. The Sponsor will inform Investigators which tumor types are open to enrollment during the conduct of Part 2.
- In Part 3, the dose and tumor type selection is based on information available from the results of all previous doses and tumor types, including information from the Phase 1 study. HNSCC has been selected for investigation in Part 3. Approximately 20 to 30 patients will be enrolled in Part 3.

All included patients will satisfy the inclusion and exclusion criteria of Part 1, Part 2 or Part 3.

species) Good Laboratory Practices (GLP) toxicology study. The planned dose range (is within the maximum allowable human equivalent dose based on all available nonclinical PK and toxicology data. Dose escalation steps of are chosen to minimize the number of cohorts likely needed to meet the objectives. If needed, a smaller step change or an intermediate dose level may be selected as the next dose. Dose levels will be evaluated only as needed.

The dose escalation phase (Part 1) is anticipated to be completed with up to

single dose of ONM-100 at X and will undergo surgery and fluorescence imaging at postdose. After the completion of surgery and imaging of Cohort A, 3 patients in Cohort B will receive a single dose of ONM-100 (for safety evaluation and surgery and imaging at If safety and the imaging feasibility for detecting primary and metastatic lymph nodes is acceptable in Cohort A and/or Cohort B, further dose escalation in Part 1 may not be necessary. Cohort C at hours postdose) and Cohort D (and imaging at hours postdose) may be included either to establish the safety margin or if the imaging results at the preceding lower dose level are sub-optimal. Smaller dose changes may be selected for doses (ie, Cohort C or Cohort D). Cohort E and Cohort F (3 patients each) may be included at 1 of the ONM-100 dose levels between to evaluate whether alternate imaging schedules postdose (ie, other than whours postdose) provide acceptable imaging results at doses Any cohort in which safety at that dose level is already established in a prior cohort in this study, or in Study ON-1001, may be enrolled for the purposes of evaluating an alternate imaging schedule postdose, in parallel to another cohort being evaluated. All dosing decisions will be made after discussing all available data between the Sponsor and Principal Investigators (PIs) and documenting the decision.

Table 1: ONM-100 Doses and Surgery/Imaging Schedules Evaluated in Part 1

 $\times \times \times \times \times \times$

| Study Part | Cohort | ONM-100 Single Dose ^a , mg/kg | Surgery / Imaging Time ª, hours | Number of Patients | Tumor Types ^b |
|---------------|-------------------------|--|--|--|--|
| | А | \times | \times | $\times\!$ | $\times\!\!\times\!\!\times\!\!\times\!\!\times\!\!\times$ |
| | В | $\times\!\!\times\!\!\times$ | \times | $\times\!$ | $\times\!\!\times\!\!\times\!\!\times\!\!\times$ |
| Part 1 | C (if needed) | $\times\!\!\times\!\!\times$ | \times | $\times\!$ | \times |
| | D (if needed) | \times | \times | $\times\!$ | $\times\!\!\times\!\!\times\!\!\times\!\!\times\!\!\times\!\!\times$ |
| | E (if needed) | $\times\!\!\times\!\!\times\!\!\times\!\!\times$ | \times | $\times\!\!\!\times\!\!\!\times$ | \times |
| | F (if needed) | \times | \times | $\times\!\!\!\times\!\!\!\times$ | $\times\!\!\times\!\!\times\!\!\times\!\!\times\!\!\times$ |
| a. | armined Resed on review | y of safety and flue | rascance data fr | | BD = to be |

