Surgical specimens obtained during the routine surgery and any ONM-100 fluorescence guided biopsies will be prepared using standard specimen processing methods and timelines. Specimens will be sampled and analyzed according to routine pathologic evaluation.

After surgery, the patient will be strictly observed following the standard, respective, postoperative protocol. Patients will be monitored for safety assessments and sample procurement.

Medical history, prior medication use, hemoglobin, and Karnofsky performance status will be evaluated at Screening and pretreatment on Day 0. Pregnancy tests will be performed at Screening and at Day 28 (\pm 5 days). Electrocardiograms (ECGs) will be performed pretreatment, at 30 \pm 10 minutes postdose on Day 0 and Day 10 (\pm 5 days).

Patient safety will be assessed for 28 days (\pm 5 days). All patients will be monitored for vital signs and physical examination pretreatment and at various time points up to Day 10 (\pm 5 days). All patients will be monitored for comprehensive metabolic panel (CMP) and complete blood count (CBC) with differentials pretreatment and at various time points up to Day 28 (\pm 5 days). All patients will be monitored for treatment-emergent adverse events (TEAEs) and concomitant medication use from the start of dosing up to Day 28 (\pm 5 days). TEAEs will be followed closely during the study to identify any potential DLTs.

Number of Patients

Up to 60 patients will be enrolled in this study (with planned allocation of up to 15 patients in up to 5 cohorts in Part 1, approximately 10 to 20 patients in Part 2, and approximately 20 to 30 patients in Part 3). The actual number of patients in Part 1 and Part 2 may vary, depending on the number of Part 1 cohorts and Part 2 Groups/tumor types that are activated for enrollment.

All patients will receive a single dose of ONM-100 followed by routine surgery and pathology of the respective solid cancer. Based on the ON-1001 study experience, we estimate that 3 patients for each dose is sufficient for safety and imaging feasibility evaluations in Part 1. Each patient's tumors will be imaged intraoperatively and at planned sites post operatively. For those patients with fluorescence in the surgical wound bed after standard procedures, tissue biopsy may be taken at surgeon's or pathologist's discretion. Up to 3 additional patients may be enrolled in the event of a DLT.

Inclusion Criteria

Patients must meet the following inclusion criteria:

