abnormal laboratory findings that are considered at least possibly related to ONM-100 will be followed until resolved or stabilized.

Criteria for Evaluation

Efficacy Analyses

In Part 1 and Part 2, ONM-100 fluorescence from in vivo and excised tissues will be imaged using intraoperative and post-operative NIR cameras and will be correlated with the histopathological confirmation of tumor and normal tissues to determine ONM-100's diagnostic performance.

In Part 3, the intraoperative fluorescence status of collected primary tumor, SOC and ONM-100 guided biopsies, as well as lymph nodes will be compared to histological analyses of the collected specimens.

Safety Analyses

Safety assessments will include the following safety related parameters:

- TEAE incidence, severity, and relationship to study drug
- Physical examination
- Vital signs
- ECGs
- Clinical laboratory (CMP, hemoglobin, and CBC with differentials)

Pharmacokinetic Analyses

Characterization of the ONM-100 PK profile will include the following major PK parameters:

- Maximum plasma concentration (C_{max})
- Time to C_{max} (T_{max})
- Area under the time-concentration curve (AUC)
- Total body clearance (CL)
- Volume of distribution (Vz)
- Volume of distribution at steady state (Vss)
- Elimination rate constant (λz)
- Terminal elimination half-life (t_{1/2})

Statistical Methods

This is a pilot study with the intention of gathering data to assess feasibility and imaging metrics for the efficacy analysis. Therefore, no formal statistical hypothesis testing will be performed for making development decisions.

Analysis populations

- Safety Population: all patients who receive any dose of ONM-100
- Efficacy Population: all patients who received any dose of ONM-100 and who have sufficient imaging and pathology analysis data to calculate fluorescence intensity and pathology correlation for ≥1 tumor sample
- Pharmacokinetic Population: all patients who receive ONM-100 and who have sufficient ONM-100
 plasma concentration data to calculate ≥1 PK parameter.

Sample Size Calculation

Given the exploratory nature of the study, formal sample size calculations were not performed.

Protocol Amendment 6.0

Safety Analyses

The safety analyses will be in the Safety Population.

Adverse events (AEs), vital signs, ECGs, and conventional clinical laboratory data (CMP and CBC with differentials) will be summarized using descriptive statistics.

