6.3 Measures Taken to Minimize Bias

Randomization, treatment allocation, and blinding are not applicable since this is a single-arm, singledose, open-label study. However, surgeons will be blinded to the presence or absence of fluorescence during standard of care surgery. Also, all pathology analyses will be blinded to the presence or absence of fluorescence, including surgical bed biopsies, tumor specimens, lymph nodes, lymph node bundles, bread loaf slices, and formalin-fixed and paraffin-embedded (FFPE) blocks.

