10.3 Pathologic Assessments

Tumor specimens will be processed for histology according to the routine pathology practice used in clinical cancer care. If an ONM-100 fluorescence tissue is not selected by routine pathological sampling, select additional samples from the fluorescence tissue for pathological correlations. As needed, an independent central pathology reading will be used for pathology assessments when data required for analysis are not provided in the standard of care report.

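### As legible, Part 3 primary sensitivity sets no rule on how a biopsy was selected; any biopsy taken because tissue fluoresced could add true positives but never false negatives

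*Protocol*

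**What the plan says.** The Part 3 objective in the protocol synopsis (Section 1.0) names sensitivity and PPV as the efficacy measures. Sensitivity is then given as "Sensitivity: True Positive Biopsies / (True Positive + False Negative Biopsies". The formula is legible in full, and no condition on the origin of a biopsy is attached to it.

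Under Criteria for Evaluation, the synopsis says of Part 3 that "the intraoperative fluorescence status of collected primary tumor, SOC and ONM-100 guided biopsies, as well as lymph nodes will be compared to histological analyses". On processing it says: "Surgical specimens obtained during the routine surgery and any ONM-100 fluorescence guided biopsies will be prepared using standard specimen processing methods and timelines".

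Three other places bear on the point:

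- Section 6.3 states that "surgeons will be blinded to the presence or absence of fluorescence during standard of care surgery", and it also blinds all pathology analyses to fluorescence.
- Section 10.3 adds sampling driven by fluorescence: "If an ONM-100 fluorescence tissue is not selected by routine pathological sampling, select additional samples from the fluorescence tissue for pathological correlations".
- A Part 3 secondary endpoint already credits additional detection by the agent: "Number of margins identified by ONM-100 and NIR imaging that could not be observed with white light and palpation alone".

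The synopsis and Sections 11.0 and 11.4 plan no formal hypothesis test.

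**The concern.** Sensitivity asks what share of tumor-positive tissue the agent lights up. That requires tumor-positive tissue sampled without regard to whether it lit up. A biopsy prompted by fluorescence fails this condition: histology can make it a true positive or a false positive, but nothing can make it a false negative. Each tumor-positive biopsy of this kind adds one to the numerator and one to the denominator, and nothing to the misses.

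The estimate would then rise with the number of guided biopsies taken, with the agent unchanged. It would depend on how readily each site takes them, across the 2 to 5 planned centers. With no test planned, the point estimate is the main reading of this endpoint, so an estimate that moves with sampling practice matters.

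**Working it through.** The protocol gives no expected sensitivity, biopsy count or sample-size calculation, so there is no figure of its own to reproduce. The check is algebra, followed by assumed inputs.

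**Algebra.** Among specimens selected independently of fluorescence, let a be the true positives and b the false negatives. Let g be the tumor-positive biopsies taken because tissue fluoresced.

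- Independent sensitivity: s = a/(a+b)
- Pooled sensitivity: (a+g)/(a+b+g)
- Difference: g·b/[(a+b)(a+b+g)]

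The difference is positive when g > 0 and b > 0, zero if either is zero, and never negative. With r = g/(a+b), the guided true positives per independent tumor-positive specimen, pooled sensitivity is (s+r)/(1+r) and the gain is r(1−s)/(1+r).

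**Size over an assumed grid** (gain in percentage points; every s and r is an assumption):

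| s | r=0.05 | r=0.10 | r=0.30 | r=0.60 |
|---|---|---|---|---|
| 0.60 | 1.9 | 3.6 | 9.2 | 15.0 |
| 0.70 | 1.4 | 2.7 | 6.9 | 11.3 |
| 0.80 | 1.0 | 1.8 | 4.6 | 7.5 |
| 0.90 | 0.5 | 0.9 | 2.3 | 3.8 |
| 0.95 | 0.2 | 0.5 | 1.2 | 1.9 |
| 1.00 | 0 | 0 | 0 | 0 |

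For example, at s=0.80 and r=0.30 the gain is 0.30 × 0.20 / 1.30 = 0.046.

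**Same agent, more guided biopsies.** Assume 16 of 20 independent tumor-positive specimens fluoresce.

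- No guided true positives: 16/20 = 80.0%
- 2 guided: 18/22 = 81.8%
- 6 guided: 22/26 = 84.6%
- 12 guided: 28/32 = 87.5%

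**A different comparator.** Let S be sensitivity over the whole surgical field. Pooled sensitivity lies below S when (s+r)/(1+r) < S, that is, when r < (S−s)/(1−S). With S=0.80 the threshold is 0.05/0.20 = 0.25 if s=0.75, and 0.10/0.20 = 0.50 if s=0.70. The upward direction is therefore certain only against s.

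**The case against.** The strongest reply is that the finding reads silence in a document with blank text. The Part 3 design paragraph in the synopsis breaks off just as it turns to sampling beyond the SOC margins. The Part 3 endpoint list in Section 5.0 is empty, the Part 3 steps in Section 9.1.4.1 are blank between anesthesia and image storage, and Appendix 3, to which Sections 11.0 and 11.4 refer, is not shown. A restriction could stand in any of these. This stands, and it makes the point conditional.

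A reader might infer that the protocol pools SOC and guided biopsies in its sensitivity. No legible sentence says so. The list under Criteria for Evaluation also covers primary tumor and lymph nodes, so it names assessed specimens and does not define the word biopsies in the endpoint. Nor does it rule out analysis by class. Likewise, the extra samples in Section 10.3 matter only if they are counted as biopsies. The synopsis remark on biopsy of a fluorescent wound bed stands in the general paragraph on patient numbers, after a Part 1 sentence, and is not a Part 3 sampling rule. If guided sampling deliberately includes non-fluorescent sites, those sites are unaffected.

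The size may also be small. Section 4.2.1.5 reports no overlap between tumor and normal fluorescence in any of the 15 Phase 1a patients. Those were ex vivo, pathologist-selected slices, so they do not settle intraoperative sensitivity, but they make s above 0.90 plausible. At s=0.95 the gain stays below 2 points for r up to 0.60.

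The blinding in Section 6.3 is not an answer. It governs how SOC surgery is done and how slides are read, whereas the problem is which tissue is sampled. Nor is this only detail left to the analysis plan, because the protocol itself fixes the formula.

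**Conclusion.** The point holds in conditional form. As legible, the endpoint admits fluorescence-triggered biopsies. If they are counted, and there is at least one guided true positive and at least one false negative among the other specimens, the reported sensitivity exceeds that in fluorescence-independent specimens. The excess is r(1−s)/(1+r): under 2 points at r=0.05 (for s of 0.60 or more) or at s of 0.95 or more with r up to 0.60, about 15 points at s=0.60 and r=0.60, and zero at s=1. Every s and r is an assumption, so the actual size is unknown.

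A reader might go further and conclude that the figure must overstate sensitivity over the whole surgical field. That does not follow. If SOC specimens under-represent easily detected tumor, the pooled figure can lie below it.

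The sponsor should make the change or point to unseen text that already restricts the set. The study is a pilot without formal testing, which limits the consequence, but sensitivity is one of its two Part 3 primary efficacy measures.

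**What to change.** Unless the blank Part 3 text or Appendix 3 already does so, state that primary sensitivity is computed on SOC specimens selected without knowledge of fluorescence. The SOC label alone may not be enough, because the Part 3 paragraph in the synopsis places further SOC margins after imaging of the excised specimen. Record two items per specimen: its origin, and whether it was chosen before fluorescence was disclosed to the surgeon. The blinding in Section 6.3 means that such a set should exist.

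Count fluorescence-triggered biopsies toward PPV and the existing secondary endpoint on margins missed by white light and palpation. Show pooled sensitivity only as a labeled supplementary figure.

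The cost is one sentence in the endpoint definition and the two data items, with no new biopsies or readers. The downside is fewer tumor-positive specimens, a wider interval and probably a lower headline figure. In the assumed example with 6 guided true positives, 22/26 = 84.6% (exact 95% CI 65.1–95.6%) becomes 16/20 = 80.0% (56.3–94.3%), ignoring clustering within patients. The restricted figure is not whole-field sensitivity either, but it does not move with the number of guided biopsies taken.

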| PPV | positive predictive value |
| SAE | serious adverse event |
| SAER | Serious Adverse Event Report |
| SBR | specimen-to-background ratio |
| SOC | standard of care |
| SOP | standard operating procedure |
| Sponsor | The sponsor is the party that commissions the organization or performance of the research, for example a pharmaceutical company, academic hospital, scientific organization or investigator. A party that provides funding for a study but does not commission it is not regarded as the sponsor, but referred to as a subsidizing party. |
| SUSAR | suspected unexpected serious adverse reaction |
| t _{1/2} | half-life |
| TBD | to be determined |
| TBR | tumor-to-background ratio |
| TEAE | treatment-emergent adverse events |
| T _{max} | time to maximum plasma concentration |
| US | United States |
| Vss | volume of distribution at steady state |

| Vz | volume of distribution at terminal phase |
|-----|--|
| WHO | World Health Organization |

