5.0 STUDY PURPOSE AND OBJECTIVES

The main purpose of this study is to investigate whether ONM-100 can be used to image primary tumors and metastatic lymph nodes at an imaging schedule earlier than 24 ± 8 hours postdose in patients undergoing routine surgery of their solid cancers and whether the diagnostic performance to detect metastatic lymph nodes can be improved by optimizing the dose and the imaging schedule.

Part 1 Primary Objectives:

- Evaluate the dose(s) at which ONM-100 fluorescence imaging is feasible
- Evaluate safety at the dose(s) used to assess imaging feasibility and select the dose(s) and imaging schedule(s)

Part 2 Primary Objectives:

Verify the safety and diagnostic performance of ONM-100 compared to standard pathology

Part 1 and Part 2 Secondary Objective

Evaluate the PK profile of ONM-100

Part 3 Primary Objective:

Assess the safety and efficacy

Part 3 Primary Endpoints:

•

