11.0 STATISTICAL METHODS

This is a pilot study with the intention of gathering data to assess feasibility and imaging metrics. Therefore, no formal statistical hypothesis testing will be performed for making development decisions. Considerations for outcome assessment are described in Appendix 3.

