11.4 Efficacy Analyses

This is a pilot study with the intention of gathering data to assess feasibility and imaging metrics for the efficacy analysis. Therefore, no formal statistical hypothesis testing will be performed for making development decisions. Considerations for outcome assessment are described in Appendix 3.

Imaging and diagnostic performance analyses will be analyzed using graphical methods and descriptive statistics.

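### The printed formula for PPV, a Part 3 primary endpoint, is wrong: the denominator lacks brackets and uses the undefined term *Tumor Positive*

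*Protocol*

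**What the plan says.** The Part 3 objective in the Protocol Synopsis (Section 1.0) is "To assess the safety and efficacy (sensitivity and positive predictive value [PPV]) of ONM-100". Two primary endpoints follow on adjacent lines:

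- "Sensitivity: True Positive Biopsies / (True Positive + False Negative Biopsies", with the closing bracket in place in the document.
- "PPV: True Positive Biopsies / Tumor Positive Biopsies + False Positive Biopsies".

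The other places where a definition could stand give none in the readable text:

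- Section 3.0 (abbreviations) expands PPV only as "positive predictive value".
- Section 5.0 has the heading "Part 3 Primary Endpoints" followed by a bullet with no readable content.
- Section 11.0 says "Considerations for outcome assessment are described in Appendix 3", and Section 11.4 repeats the reference. Appendix 3 is not in the text available for review.
- On method, Section 11.4 says only "Imaging and diagnostic performance analyses will be analyzed using graphical methods and descriptive statistics".

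**The concern.** The sensitivity line is well formed; the PPV line below it departs from the standard definition in two separate ways.

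1. **No brackets.** By ordinary operator order the line divides true positives by something and then adds the number of false positives. The result is not a proportion.
2. **A different term.** *Tumor Positive* stands where *True Positive* is needed. Part 3 compares fluorescence with histology, so *tumor positive* could naturally be taken to mean positive on histology, which is TP+FN. Under that reading, adding the brackets does not repair the line, because missed tumours enter a denominator that should hold only fluorescence-positive biopsies.

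PPV is one of two primary endpoints and is named in the Part 3 objective. The efficacy analysis is descriptive, with no formal hypothesis test, so the point estimate is itself the efficacy result. With about 20 to 30 patients in Part 3, its definition should not depend on how a reader resolves a misprint. An SAP that uses the correct formula would disagree with the protocol as printed.

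**Working it through.** The protocol states no expected PPV, no power and no formal sample size calculation, so there is no figure of its own to reproduce. The check evaluates the printed line under each possible reading. All counts and rates below are illustrative assumptions.

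**Notation.** TP, FN and FP are the numbers of true positive, false negative and false positive biopsies. Sensitivity is s = TP/(TP+FN) and the standard PPV is p = TP/(TP+FP).

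**Readings of the printed line**

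| Reading | *Tumor Positive* = TP | *Tumor Positive* = TP+FN |
|---|---|---|
| Literal, no brackets | TP/TP + FP = 1 + FP | TP/(TP+FN) + FP = s + FP |
| Brackets restored | TP/(TP+FP) = p | TP/(TP+FN+FP) |

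The literal form exceeds 1 in both columns whenever FP is at least 1 and TP is above 0. The bracketed form in the right-hand column equals PPV only when FN = 0 (for TP above 0).

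**Example 1: TP = 40, FN = 10, FP = 10**

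- Standard PPV: 40/(40+10) = 80.0%
- Bracketed, *Tumor Positive* = TP: 40/50 = 80.0%
- Bracketed, *Tumor Positive* = TP+FN: 40/(50+10) = 66.7%
- Literal: 1 + 10 = 11.0, or 0.8 + 10 = 10.8

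**Example 2: TP = 40, FN = 10, FP = 1**

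- Standard PPV: 40/41 = 97.6%
- Literal: 1 + 1 = 2.0, or 0.8 + 1 = 1.8

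**Size of the error if the term means histology-positive and brackets are supplied.** Since FN/TP = 1/s − 1 and FP/TP = 1/p − 1,

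TP/(TP+FN+FP) = 1/(1/s + 1/p − 1).

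| Assumed s | Assumed p | Value obtained | Shortfall from p (points) |
|---|---|---|---|
| 0.7 | 0.7 | 53.8% | 16.2 |
| 0.7 | 0.9 | 64.9% | 25.1 |
| 0.8 | 0.8 | 66.7% | 13.3 |
| 0.9 | 0.7 | 64.9% | 5.1 |
| 0.9 | 0.9 | 81.8% | 8.2 |

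Over a grid of s and p from 0.7 to 0.9 in steps of 0.05, the shortfall runs from 5.1 to 25.1 points.

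**After correction.** With PPV = TP/(TP+FP), the two examples give 80.0% and 97.6%, as they should.

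**Could it be a text-conversion artefact?** The brackets survive on the line directly above, *Tumor* is a whole readable word rather than a gap, and neither line shows a redaction. An authoring slip is the more likely source.

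**The case against.** The strongest case on the other side is that this is a misprint with no practical effect. The label and the objective make the intended measure plain, and PPV is a standard quantity. A literal value above 1 is impossible for a proportion and would be noticed at once. The histology-positive reading is unlikely: the sensitivity line has already written TP+FN in other words, so a new term for the same sum would be odd, and that reading contradicts the label. Under the most probable reading the numerical effect is zero. Section 5.0 is unreadable at this point, and Appendix 3 and the SAP are not available, so the correct formula may well stand in one of them.

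Much of this stands. The intent is clear, the 5.1 to 25.1 point range belongs to one less likely reading and to assumed rates, and nothing can be inferred from places that cannot be read. Any of the three could hold the right formula. These points limit the harm, but they do not make the printed line right. The finding is not that a definition is missing; it is that the protocol states a primary-endpoint formula and states it wrongly. A correct version elsewhere would leave the protocol's statements in conflict until the synopsis is amended.

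**Conclusion.** The concern holds. The Part 3 PPV formula in the Synopsis is wrong as printed in two respects, and adding brackets is enough only if *Tumor Positive* was meant as *True Positive*.

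The size depends on the reading. Bracketed and taken as a slip for *True Positive*, the bias is 0 points. Bracketed and taken as all histology-positive biopsies, the result is 5.1 to 25.1 points too low for assumed sensitivity and PPV of 70% to 90%. Taken literally, the result is not a proportion.

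A drafting slip is the probable cause. No visible sample size, test or threshold rests on the formula, and the correct PPV can be computed from the TP and FP counts at any time, so no data are lost. It should be fixed because it concerns a primary endpoint, but it is not a reason to hold up the trial.

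**What to change.** In Section 1.0, under the Part 3 primary endpoints, replace the PPV line with: *PPV: True Positive Biopsies / (True Positive + False Positive Biopsies)*. This restores the brackets, removes the undefined term and matches the form of the sensitivity line. Then check the full text of Section 5.0, Appendix 3 and the SAP for the same wording, and correct it there only if it recurs.

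The cost is one line of protocol wording, with no effect on trial operations.
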